Beyond conventional nutrients, fruits and vegetables have ubiquitous amounts of bioactive components including polyphenols, alkaloids, saponins, and terpenes and terpenoids, with polyphenols being the most ubiquitous of all. Dietary polyphenols are a diverse category of secondary plant metabolites that represent the largest group of naturally occurring antioxidants with cardioprotective benefits (7-9). A daily 5 servings intake of fruits and vegetables coincides with 500-1000 mg of total polyphenols, a threshold that is considered beneficial for cardiometabolic homeostasis (10). Our recent meta-analysis demonstrated that an average intake of 780 mg/d of total polyphenols significantly reduced blood pressure, total cholesterol, triglycerides, and improved vascular function (11). The (poly)phenolic composition of fruits and vegetables can vary considerably according to the region of growth among other factors (9, 12). For example, Africa's Indigenous Fruits and Vegetables (IFV) have been shown to contain high concentrations of polyphenols (13, 14). Our recent inventory study of Uganda's IFV with purported cardiometabolic benefits, highlighted the popularity of *Tamarindus indica* as a local adjuvant therapy for cardiometabolic risks among Ugandan communities (15). The study also revealed that the polyphenol composition of *T. indica* is superior in 4755mg/100g FW in relation to other IFV identified.

*T. indica,* is a leguminous tree belonging to the family Fabaceae with a wide range of bioactive constituents in varying levels- the highest being polyphenols followed by alkaloids, saponins, and terpenoids in that order (16). The principal flavonoids in *T. indica* fruit pulp are composed of flavanols especially the oligomeric procyanidins and their monomers- epicatechins and catechins (17, 18). Recent dietary guidelines for bioactives recommend a daily intake of 400-600 mg of flavanols for cardiometabolic protection (19) while the European Food Safety Authority (EFSA) recommends that 200 mg/d intake of cocoa flavanols is important for vascular homeostasis (20). Elsewhere, the COSMOS study showed that an intake of 500 mg/d of flavanols averts 27% of CVD mortality with significant reduction in CVD events (21). Flavanol increases the endothelial production and bioavailability of nitric oxide, a signalling molecule for endothelial function (20).

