A potential mechanism of action by which polyphenols confer hypotensive effects is by increasing the bioavailability of nitric oxide (NO) and upregulating endothelial NO-synthase activity. NO is a potent vasodilator that reduces blood pressure. Additionally, flavonoids

especially flavanols may block angiotensin converting enzyme (ACE) activity, reducing blood pressure. In fact, flavanols, anthocyanins, phenolic acids, tannins, and resveratrol have been identified as green ACE inhibitors (11).

Although the benefits of the community-based HIV care model in the resource limited HIV management settings are well documented, in Uganda, the lack of dietary interventions promoting cardiometabolic health could obscure such benefits (22-24). Lifestyle modifications such as programmed physical activity, weight loss, and dietary adjustments are indispensable to optimal cardiometabolic health (25, 26). However, the existence of a health-beauty paradox in SSA could thwart such interventions premised on maintaining a healthy body weight. The health-beauty paradox is a socio-cultural positive perception where a large body size is construed as a sign of prosperity and freedom from HIV (27). Moreover, dietary approaches that aim to add a healthy food portion on to one's habitual diet rather than completely changing their menu are by far more culturally diffusible (28). Therefore, we aim to evaluate the efficacy of *T. indica* fruit juice (added to patients' usual diets) on selected cardiometabolic risk markers of PLWH under the community-based HIV care model in Uganda in a proof-of-concept clinical trial. Evidence could lead to the concomitant use of such food products as adjuvant therapies in the secondary prevention of cardiometabolic risks.

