### 1.2. Hypotheses

The hypotheses are:

H1: Consumption of *T. indica* fruit juice will result into an overall improvement in cardiometabolic (vascular function, blood pressure, glycaemic, and lipidemic) response.

 $H_2$ : There will be differences in the dose-response relationship in cardiometabolic control following the intake of increasing doses of polyphenols in *T. indica* fruit juice.

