### 2.2 Study design and participants

This is a single centre, 2-arm, 4 weeks randomised, double-blinded parallel trial with equal allocation ratios (1:1). We will follow the Consolidated Standards of Reporting Trials (CONSORT) recommendations for randomized trials (32). Participants will be PLWH (30-60 years) managed under the community-based model (Community Drug Distribution Points-CDDPs) in Wakiso district, central Uganda. The district encircles Kampala, Uganda's capital city with an estimated population of over 2.9 million people. The district has the highest prevalence (10%) of HIV in Uganda. Over 3,801 PLWH are currently receiving the HIV care from CDDPs in Wakiso District (33). The study inclusion and exclusion criteria are presented in Table 2. The study will be announced during the drug refill days and interested patients will be provided with more information about the study before obtaining their consent to participate.

Demographic and medical information will be collected from all consented patients,

[figure not shown]
The study participants will be randomly allocated to consume twice-daily 300 mL of either 10% or 30% pulp of T. indica fruit juice, **figure 1**. Both participants and the study team will be blinded to the intervention materials. Measurements will be performed at three different timelines: 1) Baseline, 2) Week two of the study, and 3) Endline (week four of the study).

Compliance to the study protocol will be confirmed by weekly telephone inquiries, and by counting the returned empty juice bottles or unused study products at each follow-up visit. Participants will be asked to maintain their habitual dietary regimen.

Any reported unusual gastrointestinal side effects, including abdominal pain/cramps, heartburn, stomach acid/reflux, nausea, vomiting, abdominal rumbling, bloating, belching, excess gas/wind, stool type, etc, during the study will be recorded. Patients will be encouraged to contact a study staff by phone or e-mail if they experience any adverse health-related impacts of the interventions. In the case of *T. indica* fruit juice intolerance, patients will be excluded.

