# Randomisation and blinding

A biostatistician of Mildmay hospital will develop computer-generated sequence to randomly allocate participants to each of the two study arms, as shown in figure 1. The biostatistician responsible for generating the allocation sequences will not have any study-related tasks, for example, inclusion or examination of participants. The two juice prototypes will be blinded by assigning a secret code to each of the intervention products. As such, blinding of the investigators and participants will be undertaken to ensure a double-blind intervention. Moreover, the statistical analyses of the main endpoints will be done before breaking the intervention product concealment.

BP, Blood Pressure; BC, Body composition; FBG, Fasting Blood Glucose; TG, Triglycerides; Tc, Total cholesterol; PA, Physical Activity; PWV, Pulse Wave Velocity; WC, waist circumference.

Figure 1: Schematic overview of the study protocol.

Table 2: Eligibility criteria for study participants

Inclusion criteria	Exclusion criteria			
Triglycerides ≥150 mg/dL	Taking dietary supplements			
TLD regimen (ART) for ≥12 months	TB co-infection, renal failure disease, liver cirrhosis, chronic pancreatitis			
95% ART adherence in last 6 months 	Pregnancy and Lactation or regular sport activity			
Virally suppressed (most recent results viral load suppressed within the last 12 months) 	Parallel participation in another clinical trial			
PLWH aged ≥30≤60 years.	On treatment for; dyslipidaemia, hypertension or			
No plans to change location in the next 6 months	diabetes and oral hypoglycaemic drugs			
	Very low blood pressure (< 90/50 mmHg)			
	Not willing to consent or unable to consent			

ART, Antiretroviral Therapy; DBP, Diastolic blood pressure; FGD, Focus group discussion; SBP, systolic blood pressure; TLD, Tenofovir Lamivudine Dolutegravir; WC, waist circumference.

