# 2.3.1 Study outcomes

The primary endpoint will be changes in Triglycerides (TG). Secondary outcomes will include changes in fasting blood glucose and plasma levels of lipids, and parameters of vascular function, **Table 3**.

Table 3: Study outcome measures

Primary outcome measures	Secondary outcome measures	Exploratory outcomes	
Triglycerides [mg/dL]	PWV [m/s], Blood pressure [mmHg]	BMI [kg/m²]	
	Facting Pland always [mg/dI]	Fat mass composition	
	Fasting Blood glucose [mg/dL]	Waist circumference [cm]	
	HDL-c, LDL-c, Total cholesterol [mg/dL]		
	AIx (%), MAP		

BMI, Body Mass Index; PWV, Pulse Wave Velocity; HDL-c, High Density Lipoproteins; LDL-c, Low Density Lipoproteins; AIx, Augmentation Index; MAP, Mean Arterial Pressure

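### Blood pressure below 90/50 mmHg bars entry and the juice is expected to lower pressure, yet no count of low readings and no recording rule for non-gastrointestinal symptoms is planned

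*Combined protocol and SAP*

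**What the plan says.** Table 2, under the heading Randomisation and blinding, lists "Very low blood pressure (< 90/50 mmHg" among the exclusions, with no rationale. The same table excludes people on treatment for hypertension.

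Section 1.1 expects pressure to fall. It states: "A potential mechanism of action by which polyphenols confer hypotensive effects is by increasing the bioavailability of nitric oxide (NO". It adds that flavonoids, "especially flavanols may block angiotensin converting enzyme (ACE) activity, reducing blood pressure", and cites the authors' meta-analysis, in which "an average intake of 780 mg/d of total polyphenols significantly reduced blood pressure". Hypothesis H1 in section 1.2 predicts improvement in "cardiometabolic (vascular function, blood pressure, glycaemic, and lipidemic) response".

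Under section 2.2 all participants "consume twice-daily 300 mL of either 10% or 30% pulp" juice, so neither arm is juice-free. The schedule is: "Measurements will be performed at three different timelines: 1) Baseline, 2) Week two of the study, and 3) Endline (week four of the study".

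Table 3 in section 2.3.1 places "PWV [m/s], Blood pressure [mmHg" among the secondary outcomes and lists no safety outcome. Section 6 summarises continuous variables by mean and standard deviation and compares groups by t-test, with linear mixed models for missing data.

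On harms, section 2.2 says reported gastrointestinal effects will be recorded, encourages patients to contact staff by phone or e-mail about adverse health effects more generally, and excludes those who do not tolerate the juice. Intolerance is not defined. Section 10 covers only withdrawal at the participant's own wish.

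**The concern.** The plan sets a lower limit on blood pressure at the door, gives everyone a product that it expects to lower pressure, and then measures pressure twice more. It does not say what a later reading below its own limit means. Such a reading enters the arm mean and is not counted as a possible harm. Symptoms that might accompany it, such as dizziness or fainting, fall outside the one class of side effect that the protocol undertakes to record.

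What is at stake is how well harms are ascertained and reported. A reader of the results could not tell whether a lower mean reflects modest lowering across participants or includes some with very low pressure. Because both arms drink juice, a fall common to both also cancels in the between-arm comparison of section 6. A count per arm would show such cases.

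**Working it through.** The documents state no sample size, effect size or blood pressure variability, so there is no planned figure to reproduce. The check is a trace of the text followed by three small calculations.

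**1. Where blood pressure appears after entry**

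| Place | Content | Uses the 90/50 floor? |
|---|---|---|
| Table 2 | Exclusion at entry | Yes, at entry only |
| Section 2.2 | Measurements at baseline, week two, week four | No |
| Table 3 | Secondary outcome in mmHg | No |
| Section 2.4.2.2 | How to read it; extra readings if two differ by more than 5 mmHg | No |
| Section 6 | Mean, standard deviation, group comparison | No |
| Section 10 | Participant-initiated withdrawal | No |

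Figure 1 is not shown in the text available, so the blood pressure schedule rests on the general statement in section 2.2.

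**2. Whether the floor is defined well enough to count against**

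A person with systolic pressure below 90 and diastolic pressure at or above 50 is excluded if either low value suffices and admitted if both are needed. Table 2 does not say which. It also names no device or posture. Section 2.4.2.2, headed as blood pressure, uses a seated left-arm monitor. Section 2.4.2.1 takes two further pressures with the Arteriograph, supine on the right arm, to derive mean arterial pressure. The headings suggest the former, but Table 2 does not refer to either.

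**3. Dose against the documents' own benchmark**

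Inputs: total polyphenols per 100 mL from Table 1 (8.30 and 26.36 mg); daily volume 2 × 300 = 600 mL from section 2.2; 780 mg/d from section 1.1.

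- 10% juice: 8.30 × 6 = 49.8 mg/day; 49.8 / 780 = 6.4%.
- 30% juice: 26.36 × 6 = 158.2 mg/day; 158.2 / 780 = 20.3%.

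The documents therefore support the expected direction of effect but not a large fall.

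**4. How a mean absorbs one low reading**

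Illustration only: one participant goes from 91 to 84 mmHg systolic in an arm assumed to hold 20 people. The arm mean moves by (91 − 84) / 20 = 0.35 mmHg. The crossing of the floor cannot be seen in the mean.

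**5. Chance that there is anything to count**

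Assumptions, since the documents give neither figure: total N of 20 to 100, and a true rate p of 1% to 5% below the floor. The chance of at least one such participant is 1 − (1 − p)^N.

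| Total N | p = 1% | p = 5% |
|---|---|---|
| 20 | 18% | 64% |
| 40 | 33% | 87% |
| 100 | 63% | 99% |

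Even at low rates, one or more cases is plausible in a small trial.

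**The case against.** An exclusion criterion governs entry, so the plan does not formally contradict itself by not repeating the floor later. Blood pressure lowering is presented as a benefit. The dose is a small fraction of the benchmark, and excluding people on antihypertensive treatment removes the obvious additive risk. Section 2.4.2.2 accepts differences of up to 5 mmHg between readings, so some readings below the floor would be noise. Individual values are kept, and counts could be derived later. All of this stands. It lowers the likely frequency and the weight of the point, but it supplies neither a planned count nor a recording rule.

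A reader might infer more than the documents support:

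- **That symptoms have no route to the study team.** Section 2.2 invites contact about adverse health effects of any kind. What is missing is a rule for recording what is reported.
- **That a participant with a low week-two reading is handed more juice.** No dispensing schedule is given; section 2.2 mentions only bottle counts at follow-up visits.
- **That hypotension is the plan's one expected pharmacological harm.** Table 2 gives no reason for the floor, and the side effects actually listed are gastrointestinal.
- **That about two thirds of participants have no raised pressure to lower.** The survey in section 1.1 gives 31.5% with high blood pressure, hence 100 − 31.5 = 68.5% without. That sample was not selected on triglycerides as this trial's will be, and lacking high pressure is not the same as being near 90/50.
- **That small falls will commonly cross the floor.** Someone entering at 90 to 95 mmHg systolic needs a fall of only 1 to 6 mmHg to read 89, but nothing shows how many people enter in that range.

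**Conclusion.** The point holds as a gap in safety ascertainment and reporting. The floor is an entry criterion only. Later readings serve as a secondary efficacy mean, no count below the floor is planned, and no recording rule covers non-gastrointestinal symptoms. Reading the floor as a safety limit is an inference, though the natural one.

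The size is modest. At about 50 and 158 mg/day, 6.4% and 20.3% of the 780 mg/d cited, large falls are not supported, and no frequency can be estimated from the documents. The dose comparison assumes that Table 1 describes the juice as consumed and that 780 mg/d is a fair yardstick; it is an average intake from a meta-analysis, not a threshold. The documents do not support calling the trial unsafe. They support a cheap improvement, made before data collection, that lets the trial show whether low pressure occurred and in which arm.

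**What to change.** 1. Reconcile Table 2 with sections 2.2 and 2.4.2.2. State whether the 90/50 floor means either value or both, which of the planned readings it refers to, and whether it has any role after randomisation. These choices, and any clinical response to a low reading, belong to the sponsor and investigators.
2. Add to section 2.3.1 and section 6 a safety outcome: the number of participants in each arm below the plan's own floor at week two and at week four, on the definition fixed in item 1, with the number measured as denominator. With both arms on juice and no stated sample size, present it descriptively.
3. In section 2.2, record non-gastrointestinal symptoms such as dizziness or fainting on the weekly calls already planned, asked the same way in both arms, and say how contacts initiated by participants are recorded.

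The cost is a few sentences, one more table row and slightly longer calls. The readings and the calls are already in the plan.

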# 2.3.1 Study outcomes

The primary endpoint will be changes in Triglycerides (TG). Secondary outcomes will include changes in fasting blood glucose and plasma levels of lipids, and parameters of vascular function, **Table 3**.

Table 3: Study outcome measures

Primary outcome measures	Secondary outcome measures	Exploratory outcomes	
Triglycerides [mg/dL]	PWV [m/s], Blood pressure [mmHg]	BMI [kg/m²]	
	Facting Pland always [mg/dI]	Fat mass composition	
	Fasting Blood glucose [mg/dL]	Waist circumference [cm]	
	HDL-c, LDL-c, Total cholesterol [mg/dL]		
	AIx (%), MAP		

BMI, Body Mass Index; PWV, Pulse Wave Velocity; HDL-c, High Density Lipoproteins; LDL-c, Low Density Lipoproteins; AIx, Augmentation Index; MAP, Mean Arterial Pressure

# 2.4 Protocols for measuring study outcomes.

#### 2.4.1 Biochemical Measurements

CardioChek Plus will be used to assess fasting blood glucose and lipid profile (total cholesterol, HDL-c, LDL-c, and triglycerides). It is an on-site test which gives results in as little as 90 seconds. The CardioChek plus is patient friendly in that it requires a fingerstick blood sampling

<sup>1In line with the national guidelines for community drug distribution points (Community care model for HIV), WHO stages 1 or 2 (34).

of 15 to 40  $\mu$ L. Participant safety is guaranteed; the trained laboratory technician handling the testing will sanitize and wear cloves while doing the test, the participants finger (middle or ring finger) will be cleansed with an alcohol wipe for at least 30 seconds and the stick will always be on the side of the finger rather than the tip. The testing will be performed by trained laboratory technician. Participants will be requested to fast overnight and not to indulge in exercise in the morning. To ensure this, tests will be carried out early morning before breakfast.

# 2.4.2 Parameters of vascular function

### 2.4.2.1 Pulse wave velocity, Mean arterial Pressure, and Augmentation Index

Increased arterial stiffness, measured non-invasively by a rtic pulse wave velocity (PWV), is one of the earliest detectable manifestations of adverse structural and functional changes of the vessel wall (35). Aortic PWV will be estimated twice in the supine position on the right upper arm, using the validated Arteriograph device (TensioMed, Budapest, Hungary) (36). The Arteriograph is an operator-independent, non-invasive device that uses an oscillometric occlusive technique to estimate the aortic PWV and AIx. In short, after two conventional BP measurements, the Arteriograph produces a cuff pressure over the brachial artery that is 35 mmHg in excess of the systolic blood pressure measured. This suprasystolic pressure is used to analyse the pulse wave. To calculate the PWV, the distance from the jugulum to the symphysis is measured in a straight line using a tape measure, as a surrogate measure of the aortic length, and multiplied by two. The result is then divided by the difference in time between the beginning of the first wave and the beginning of the second (reflected) wave, resulting in the PWV in meters per second (m/s) (36, 37). The two conventional BP measurements of the Arteriograph will be used to calculate the mean arterial pressure (MAP). The AIx corresponds to the pressure difference (amplitude difference; P1-P2) between the first and second wave in relation to the pulse pressure (PP). The Arteriograph calculates the AIx on the basis of the formula, AIx% = [(P2-P1)/PP] \*100 and thus provides the brachial AIx without applying a transfer function (37). In order to standardize the measurement, we will use the protocol provided by the manufacturer. At the end of every examination day, data will be directly exported from the Arteriograph output into SPSS, preventing data-entry errors.

# 2.4.2.2 Blood pressure

Blood pressure will be measured using blood pressure monitor – Seca b12. Blood pressure measurements will be taken on the left arm with the participant in a sitting position (after a five-minute rest in sitting position). Two readings will be taken at least one minute apart and the mean of the last two readings will be taken as the final blood pressure. In case of there's

more than a 5-mm Hg difference between the first and second readings, additional readings will be obtained and then the mean value of these multiple readings will be used (38).

## 2.4.3 Anthropometrics

Height will be taken to the nearest 0.1 cm using a portable stadiometer. Weight will be measured to the nearest 0.1 kg using the Seca 874 dr weighing scale. Participants will remove shoes and heavy clothing (jackets) and pocket items before measurements. Weight and height measurements will be used to calculate BMI (kg/m²). Waist circumference (to the nearest 0.5 cm) will be measured using a non-stretchable standard tape measure (gulick measuring tape). The waist measurement will be taken at the level of the iliac crest with the participant standing, at the end of gentle expiration (39).

# 2.4.4 Body composition measurement

Body composition will be measured using Bodystat 1500 lite touch. This equipment uses the scientifically validated principle of bio-electrical impedance analysis, to measure body composition parameters namely, fat, lean weight, optimal total body weight range and body water levels, is instantly displayed on the screen of the Bodystat 1500 lite touch. The measurement is not recommended after strenuous exercise. The body would have lost excessive fluid through sweat, and an abnormally low fluid level would increase the impedance measurement resulting in an artificially higher percent fat than would normally be the case. Therefore, participants will be advised to avoid strenuous activities on the day of measurement. To ensure this, tests will be carried out early morning before breakfast.

